7.3 TRIAL DATABASE

The Stroke Trials Unit, Nottingham (STUN) will provide a bespoke trial database with electronic case report forms. It will contain one database for the pseudonymised data and one to encrypt and store participants' personal identifiable data.

The data will be held on the University of Nottingham's servers/storage, which are based at the King's Meadow campus and protected by regular security updates and firewall software.

Data will be entered into the eCRF by site investigators and central follow-up co-ordinators who are fully trained and delegated to access e-CRFs. Each research team member will receive unique login credentials to access only relevant parts of the database.

The Systematic Image Review System Tool (SIRS) will be used as a web-based imaging database to assess the brain scans. The SIRS is comprised of the imaging database, which will be accessed only by the members of the central team and will be hosted by the servers located at the University of Edinburgh Data Centre on the King's Buildings Campus, and the web application that scans readers will use to access their assigned cases. The web application accesses rendered views of imaging and not the imaging database itself. Scan reads are transferred to the University of Nottingham to link with the eCRF for statistical analysis.

Trial database will be achieved after the end of trial and stored on University of Edinburgh servers for a minimum of five years.

8. DATA MANAGEMENT

8.1 Data Management Plan

All aspects of data collection, data processing (entry/uploading, cleaning, and query management), and the production of the final dataset ready for analysis and/or archiving will be detailed in a separate Data Management Plan (DMP).

8.2 Personal Data

All investigators and the central trial staff must comply with the Data Protection Act and the General Data Protection Regulation (GDPR). Access to identifiable participant data will be limited to the research team, sponsor representatives, and regulatory authorities.

The following personal identifiable data will be collected as part of the research:

The following personal identifiable data will be collected as part of the research: forename, surname, initials, date of birth, sex assigned at birth, ethnicity, socioeconomic information (years of education, occupation), home address, telephone numbers, email addresses, contact information for the close personal contacts, GP address, unique healthcare identifiers like CHI/NHS Number and medical history.

The participant's name and contact details will help to facilitate contact during the follow-up by phone and post. The local investigators and central trial coordinators will collect the information on safety, outcomes and drug adherence. The local research teams will post a study drug if applicable to the participant's home address.

A patient's initials, age, sex and years of education are part of the electronic baseline data and are required for randomisation procedures. Patient initials alone will be recorded as a safeguard against duplicate entries on e-CRF.

Demographic information such date of birth, sex assigned at birth, ethnicity, socioeconomic information (years of education, occupation) will help to study whether those characteristics influence the effects of the tested drugs.

Participant's GP address is required to inform about the participant's involvement in LACI-3 and the treatment allocation. The GP letter will include participant's name, address, date of birth and CHI/NHS Number to verify that we are communicating about the correct participant with GP.

Participant's relatives, carers, or close personal contacts information will be used if the participant cannot be contacted or the participant no longer has the mental capacity to make decisions for themselves during the follow-up.

The site investigators and central trial teams at the University of Edinburgh and the University of Nottingham will process personal data. Research teams will store personal data on password-protected computers at sites kept in locked offices. The trial documentation containing personal data will be stored and kept in locked and secured filing cabinets within secure alarmed buildings. Access to trial documentation will be restricted to the trial team exclusively.

Published results will not contain any personal data that could allow identification of individual participants.

8.3 Data Information Flow

The data collection and access will occur through Case Report Forms (CRFs). The site investigators will upload participant data into the trial database, where the data will be stored. During the follow-up, the local research teams and the central trial coordinators will access data to enable contact with participants and collect information for the follow-up visits. They will record and report data on electronic CRFs. The access to the database will be locked after the trial is compete and ready to be archived. Anonymised and de-identified data may be available for data sharing after obtaining applicable approvals.

8.4 Data Storage

Personal data will be physically stored by the research teams within locked filing cabinets in locked offices, with swipe card access for authorised personnel only.

The research teams will digitally store personal data using password-protected database logins to access the trial database. The database servers are hosted in a secure server room within the King's Meadow Campus at the University of Nottingham. Access to the secure server room is restricted to authorised individuals with swipe card access and pin codes.

8.5 Data Retention

Personal data will be stored for a minimum of five years and destroyed only with permission from the chief investigator and sponsor. The anonymised dataset will be securely stored in the Data Vault, the University of Edinburgh's archival storage platform.

Trial documentation may be destroyed only after the minimum retention period with permission from the chief investigator and the Sponsor.

8.6 External Transfer of Data

Data collected or generated by the study (including personal data) will not be transferred to any external individuals or organisations outside of the Sponsoring organisation(s) and the University of Nottingham.

8.7 Data Controller

A data controller is an organisation that determines the purposes for which, and the manner in which, any personal data are processed.

The University of Edinburgh and NHS Lothian are joint data controllers along with any other entities involved in delivering the study that may be a data controller in accordance with applicable laws (e.g. the site).

The LACI-3 is run by the University of Edinburgh and the University of Nottingham who provides the trial database and acts as data processor.

8.8 Data Breaches

Any data breaches will be reported to the University of Edinburgh ([contact]) and NHS Lothian ([contact]) Data Protection Officers who will onward report to the relevant authority according to the appropriate timelines if required.

9. STATISTICS AND DATA ANALYSIS

9.1 SAMPLE SIZE CALCULATION

The primary outcome, cognitive impairment assessed using the DSM-5 7-level ordinal score, will be compared between ISMN vs no ISMN, cilostazol vs no cilostazol, and ISMN+cilostazol vs no ISMN or cilostazol using ordinal logistic regression adjusted for stratification and minimisation variables. The null hypothesis is that ISMN, alone or with cilostazol, will not reduce long-term cognitive impairment in patients with lacunar ischaemic stroke.

A sample of N=1300 is needed (650 ISMN, 650 no ISMN) assuming alpha 5%, power 90%; distribution of DSM-5 7-level ordinal score in the control (standard of care) group is: level 1 (normal): 35%, 2: 24%, 3: 12%, 4: 20%, 5: 3%, 6: 3%, 7 (dead):3% (as in LACI-2); DSM-5 7-level unadjusted odds ratio 0.70 (the risk reduction exceeds the minimal clinically important

difference [MCID] of 0.27), standard deviation 1.33; losses/cross-overs 15%; no covariate adjustment; sample rounded up

Notes:

1. We chose OR 0.70 because it represents a 'small' treatment effect and so is of relevance to the large lacunar stroke cSVD population; a readily available, easy to administer and inexpensive intervention, albeit with small (or better) effect, would be very valuable clinically. The odds ratio=0.70 is more conservative than that seen in LACI-2: ISMN vs no ISMN aOR 0.55 (95% CI 0.36, 0.86) and ISMN+cilostazol aOR 0.44(95%CI 0.23-0.85).⁴⁹

2. The MCID assumption of 0.27 lies in the range of 0.17 to 0.69, which is based on plausible values from anchor, distribution and expert opinion in dementia and stroke studies,⁶¹⁻⁶⁴ and calculated from LACI-2⁴⁹ and R4VaD, a large UK cohort study, n=2441, of post-stroke cognitive impairment.⁴⁸ The distribution-based MCID of 0.27 is based on pooled standard deviation (SD) of 1.33 in LACI-2, multiplied by 0.2, as appropriate for low cost drugs.⁶¹ The anchor-based MCID for DSM-5 7-level cognition at 1year in LACI-2 was 0.41 for ISMN v no ISMN,⁴⁹ and was 0.69 for severe vs. mild stroke in R4VaD, but this is less relevant to lacunar stroke (1^{ry} results in prep).⁴⁸ A survey of experts (n=48, ongoing) suggested an MCID of median 0.4-0.5.

3. LACI-2 showed no differential loss between treatment groups using telephone/postal followup,⁴⁹ a common issue in cognition trials. We assume losses of up to 15%, within rates seen previously (8-15%).^{27,49} We do not expect cross-overs since ISMN and cilostazol are rarely used in the UK after lacunar stroke.

4. We and others have shown that adjustment for co-variates improves statistical power⁶⁵ and so can reduce sample size; we have not taken account of this in the above sample size calculation since the relevance of these findings to analysis of ordinal cognitive scales remains unclear. However, covariate adjustment will likely improve statistical power so that the final power will probably be greater than assumed here.

5. The number needed to treat is 6.1 (95%CI 3.7, 17.2) which is very potent for a prevention trial.

6. The power varies by the final achieved sample size (Table 2)

Table Power	95%	90%	85%	80%	75%	70%	65%
Total sample size ISMN vs no ISMN	1521	1229	1052	918	812	723	644

9.2 PROPOSED ANALYSES

All analyses and presentation of the results will be in accordance with CONSORT guidelines including on factorial trials.⁶⁶ All analyses will be intention to treat. A full statistical analysis plan will be developed and published prior to database lock including use of imputation or complete case analysis and sensitivity analyses. Numbers (%), median [interquartile range] or mean (SD) will be used as appropriate to summarise data, with 95% confidence intervals (CI). Main outcomes will be presented for the whole population and by sex. Participants who die will be included in the DSM-5 7 level ordinal cognitive and mRS scores, and for scores without a category for death will have a score worse than any living score assigned to maintain power and prevent missing any 'kill or cure' effect. Multiple testing adjustments will be used where relevant.

Analyses will use, as appropriate: binary logistic regression (BLR, presented as adjusted odds ratio, aOR), Cox proportional hazards regression (CPHR, adjusted hazard ratio, aHR), ordinal logistic regression (OLR, presented as aOR), or multiple linear regression (MLR, presented as adjusted mean difference, aMD). 95% confidence intervals (CI) will also be given.

Analyses will be adjusted for stratification (MoCA) and minimization variables (baseline age, sex, NIHSS, mRS, SBP, smoking status, time after stroke, years of education). Additional adjustments will be used where relevant and feasible, e.g. treatment duration, visible infarct y/n and SVD burden.

The Primary outcome is an ordinal adjusted analysis of the DSM-5 7-level cognitive score at 18 months.

Secondary outcomes will be analysed including all available data, using:

-*MLR*: 7-level ordinal mRS, 4-level DSM-5 cognitive score, cognitive tests individually (MoCA, TICS); Quality of Life (EQ-5D, Health Status Utility Value and VAS); mood (Zung); Stroke Impact Scale individual domains and overall score;

-BLR: dependency [mRS>2] vs no dependency; death; recurrent ischaemic or haemorrhagic stroke or TIA, or MI, individually; systemic haemorrhage; symptoms; SAEs, SARs, SUSARS – events that meet these definitions as per protocol and that are not already reported as formal outcomes;

-CPHR: death; and a Composite Outcome (recurrent stroke or TIA, MI, dependency [mRS>2], any cognitive impairment, death) using patients with complete data for all required variables, adjusted for baseline variables;

-and the *Wei-Lachin test* (unadjusted), reported as *Mann-Whitney difference (MWD)*: a Global Clinical Outcome (recurrent ordinal stroke, ordinal MI, ordinal 7-level cognition, ordinal mRS, quality of life (full Health Status Utility Score of the EQ-5D), the Zung depression score full scale, and the binary status of alive or dead) using all patients; and a Global SIS score.

Subgroup analyses: Prespecified subgroups include all minimisation variables (baseline age, sex, NIHSS, mRS, SBP, smoking status, time after stroke, and years of education), hypertension, diabetes, prior stroke/TIA, index infarct on imaging, WMH score, SVD score, duration of treatment, for 7-level ordinal cognition, ordinal mRS, recurrent stroke or TIA. We will assess cognitive and dependency outcomes, recurrent vascular events, safety, QoL and HE usage at 6 and 12 months, using repeated measures where relevant. Subgroup analyses will be adjusted for cilostazol in ISMN models and for ISMN in cilostazol models to assess interactions. Other exploratory subgroup analyses may be performed.

Sensitivity analyses: Imputation analysis of primary outcome. Baseline characteristics of participants with versus without long term outcome cognition data (DSM-5 7 level ordinal score, tMoCA, TICS) and/or long-term dependency (mRS) to assess for drop-out bias. Composite Outcome, including all patients with any data for the required analysis, regardless of whether missing.

Missing data: The primary outcome (DSM-5) incorporates data from multiple sources and so suffers from less loss of data than when using a single outcome scale; Death is a valid outcome in DSM-5 and is not missing data; The sample size includes an inflationary adjustment for up to 15% missing primary outcome data; Baseline data and adherence will be compared for those with versus those without missing DSM-5 data.

A full Statistical Analysis Plan will be prepared and published during LACI-3 prior to data softlock, as was done for LACI-2, and will describe analysis procedures and procedures for missing, unused or spurious data, and definitions of populations analysed.

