3. STUDY DESIGN

LACI-3 will be an investigator-led, Phase III, prospective, randomised, controlled, 2x2 partial factorial, open label, blinded outcome trial performed in multiple UK hospital-based centres. LACI-3 is open to support international collaboration. The trial received Scientific Advice from the Medicines and Health Care Regulatory Agency assisted by NHS England Medicines Repurposing Programme at a meeting on 2nd July 2024. All MHRA guidance has been incorporated into the design of LACI-3.

Duration: The trial will last for 52 months with the treatment phase for each participant starting from within one day of randomisation until the end of trial follow-up at 18 months.

Participants meeting inclusion/exclusion criteria will be randomised at participating hospitals.

Participants will be randomised to start one of four treatments; ISMN only; cilostazol only; both ISMN and cilostazol; or neither ISMN nor cilostazol. Patients with contraindications to cilostazol can be randomised to ISMN versus no ISMN arms only; patients with contraindications to ISMN can be randomised to cilostazol versus no cilostazol arms only. The partial factorial design allows testing of both drugs when given alone and together. As in LACI-2, the doses will be escalated until participants are on their full dose by 1 month. If a patient encounters intolerable side effects at full dose, then they will be able to remain on the highest dose regime that they can tolerate and this dose will be recorded. The total duration of the trial drug administration will be 18 months. After the end of follow-up, the patients will reduce the tablets over about two weeks and then stop the trial medication. They will return any unused drug to their local community pharmacy or the hospital pharmacy if more convenient for destruction.

Drug supply: Trial drug will be dispensed by hospital pharmacies. The first drug supply will be given at the randomisation visit if allocated to the IMP. The IMP re-supply for the followup at 6 and 12 months will be posted to participants. Participants can collect the IMP resupply in person from the recruiting site.

Participants should continue their allocated treatment until the end of 18-month follow-up.

Discontinuing the allocated treatment by the participant's direct clinical care team due to the occurrence of an outcome event does not constitute withdrawal.

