5.6 WITHDRAWAL OF STUDY PARTICIPANTS

Participants are free to withdraw from the study at any point or a participant can be withdrawn by the Investigator. If withdrawal occurs, the primary reason for withdrawal will be documented in the participant's case record form if possible. The participant will have the option of withdrawal from:

- (i) study medication with continued study procedures and collection of clinical and safety data;
- (ii) study medication and follow-up visits (or study procedures) with continued collection of clinical and safety data from medical notes
- (iii) Consent to be contacted about other research studies
- (iv) all aspects of the trial but continued use of data collected up to that point. To safeguard rights, the minimum personally identifiable information possible will be retained.

Randomised patients who wish to be withdrawn from the study before they have undertaken any study related procedures will be withdrawn from the study and

another participant will be recruited to replace them. Data on the original participant will be kept on the CRF/database if the participant agrees to this.

Trial medication may be stopped at any time by the Investigator or treating physician if deemed advisable. Stopping trial medication on its own does not necessarily equate with withdrawal from the trial, and follow-up procedures will continue unless the participant withdraws consent. Participants who wish to withdraw from follow-up will not be able to continue on the IMP. Participants may wish to withdraw from active participation in follow-up by central co-ordinators but agree that relevant information can be obtained from their hospital or GP records. Participants may withdraw consent to be contacted about other research but this will not affect their continued participation in LACI-3. These scenarios will be documented and kept up to date in the CRF.

If after randomisation into LACI-3, a participant subsequently is found to have a condition which would have made them ineligible for recruitment, these participants will be retained in the trial, at least for the purposes of follow-up, to protect the 'intention to treat' principle of analysis, and a decision for the continuation of the IMP will be made by the Principal Investigator or designee with the participant (or their relatives in the event of loss of capacity) on the basis of safety.

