The lifestyle risk factors for vascular disease such as cigarettes and alcohol use as well as blood pressure, weight and height will be collected as a part of the baseline information.

Participants will be asked about health-related quality of life (using the EuroQol Group EQ-5D-5L/ EQ-VAS instrument).

Haematology and biochemistry: Full blood count, urea and electrolytes and renal function results will be obtained and collected on e-CRF from the most recent standard of care results sample since the time of the index stroke. If there is a clinical reason to expect change since this last sample, the full blood count and biochemistry should be repeated prior to randomisation. These samples will be analysed in the hospital haematology or biochemistry labs in the centre in which the patient has been recruited as a part of the standard clinical care.

Clinical outcomes: Information on recurrent ischaemic stroke, TIA, major systemic or brain haemorrhage, non-fatal MI, and dementia will be assessed by phone or post questionnaire at 6, 12, and 18 months as well as by checking the participant's medical notes. Patients will be encouraged to seek medical advice if they develop new neurological events during the trial. The death of any cause will be detected, reported and recorded by the investigators based on the information from the medical notes.

Functional outcome: modified Rankin Scale to assess dependency at 6, and 12, 18 months. If participants are unable to be contacted, the central assessor will obtain the most recent modified Rankin Score from the local staff (if available) or estimate from the relative/carer.

Cognitive and mood outcomes: Telephone MoCA (tMoCA), The Telephone Interview for Cognitive Status (TICS), animal naming, Concentration (from the MMSE), the ZUNG and Stroke Impact Scale (SIS), will be collected remotely at 6, 12 and 18 months by the central trial team.

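### Section 9.2 uses treatment duration, which arises only after randomisation, as a prespecified subgroup and an optional covariate; both uses would break the intention-to-treat comparison.

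*Protocol*

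**What the plan says.** Section 9.2 states the principle first: "All analyses will be intention to treat". It requires adjustment for baseline MoCA and the minimisation factors, and then opens a further option: "Additional adjustments will be used where relevant and feasible, e.g. treatment duration, visible infarct y/n and SVD burden". The same section's list of prespecified subgroups ends with "index infarct on imaging, WMH score, SVD score, duration of treatment, for 7-level ordinal cognition, ordinal mRS, recurrent stroke or TIA". No condition is attached to that list.

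Section 3 fixes the planned exposure: "The total duration of the trial drug administration will be 18 months". Section 5.6 allows it to be cut short: "Trial medication may be stopped at any time by the Investigator or treating physician if deemed advisable". Sections 6.2 and 6.3 show that there is no placebo and that the group allocated neither drug takes nothing throughout.

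Section 9.1 describes the primary analysis as an ordinal logistic model whose covariates are the randomisation stratifier and the minimisation factors. Treatment duration is not among them.

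On quality of life, Section 6.9 says of the baseline visit: "Participants will be asked about health-related quality of life (using the EuroQol Group EQ-5D-5L/ EQ-VAS instrument". The baseline values do not appear in the Section 9.2 adjustment set.

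**The concern.** A covariate or subgroup factor in a randomised comparison should be fixed before allocation. Time on treatment is not. It is shortened by intolerance, by clinical events, by withdrawal and by death, and each of these may depend on the drug, on the patient's prognosis, or on both. Holding it constant, or splitting by it, compares people who differ for reasons other than allocation.

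The outcomes chosen for the subgroup make this worse. Death is the worst level of the 7-level cognitive scale and also ends treatment. Recurrent stroke or TIA is an outcome to be examined by duration, while Section 3 expects that treatment may be discontinued because an outcome event has occurred. The outcome can therefore determine the subgroup.

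At stake are the credibility of a prespecified subgroup on the primary scale, and the drug effect in any model that uses the optional term. The trial is meant to support a licence extension, so an open option of this kind is undesirable.

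**Working it through.** **1. What the variable can be.** There are two readings, and neither is usable.

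- Planned duration: 18 months for every participant (Section 3). It is a constant, so it can be neither a covariate nor a subgroup factor.
- Realised duration: known only after randomisation. It is undefined for the group allocated neither drug (Sections 6.2 and 6.3). The document says neither how to code that group nor, for those on both drugs, whose duration counts.

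**2. The plan's own figure, to confirm the inputs.** Section 9.1 gives a control distribution of 35/24/12/20/3/3/3%, an odds ratio (OR) of 0.70, power 90%, alpha 5% (taken as two-sided) and 15% losses. The proportional-odds formula is N = 12(z₀.₉₇₅ + z₀.₉₀)² / [(ln 0.70)²(1 − Σp̄³)], where p̄ is the mean of the two arms' distributions.

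- Base N = 1,079. Dividing by 0.85 gives 1,270, consistent with the stated 1,300. Multiplying by 1.15 gives 1,241, close to the power table's 1,229.
- Power at 1,300 with 15% lost is 90.7%.
- The calculation assumes no covariate adjustment, so the present point does not change N.

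**3. Illustrative simulation.** Each scenario has 60,000 participants, with ISMN and cilostazol allocated independently 1:1 and cilostazol given no effect. Cut-points come from the Section 9.1 distribution. The following are assumptions that the document does not give:

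- a latent frailty score that raises the log-odds of a worse outcome by 0.5 or 1.0 per SD;
- early stopping in 15% or 25% at average frailty, with log-odds rising 0.8 per SD of frailty;
- stopping times uniform over 18 months, and death truncating duration.

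Entries are fitted ORs for ISMN versus no ISMN.

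| True OR | Frailty | Stopping | ITT | + any-drug duration, neither = 0 | + ISMN duration, no ISMN = 0 | + duration, neither = 18 months | Full-duration ISMN vs all no ISMN | Short-duration ISMN vs all no ISMN |
|---|---|---|---|---|---|---|---|---|
| 1.0 | 0.5 | 15% | 0.993 | 1.154 | 3.434 | 0.938 | 0.844 | 1.981 |
| 1.0 | 0.5 | 25% | 1.007 | 1.193 | 2.519 | 0.942 | 0.822 | 1.651 |
| 1.0 | 1.0 | 15% | 1.028 | 1.317 | 5.956 | 0.940 | 0.806 | 2.710 |
| 1.0 | 1.0 | 25% | 1.003 | 1.295 | 3.730 | 0.905 | 0.747 | 2.017 |
| 0.70 | 0.5 | 15% | 0.718 | 0.837 | 1.849 | 0.681 | 0.624 | 1.277 |
| 0.70 | 0.5 | 25% | 0.711 | 0.821 | 1.480 | 0.666 | 0.596 | 1.080 |
| 0.70 | 1.0 | 15% | 0.761 | 0.948 | 3.477 | 0.702 | 0.612 | 1.800 |
| 0.70 | 1.0 | 25% | 0.732 | 0.902 | 2.275 | 0.660 | 0.555 | 1.387 |

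Without duration, the model recovers the null (0.99 to 1.03). With a true conditional OR of 0.70 it gives 0.71 to 0.76; the shift towards 1 reflects the unmodelled frailty, not bias from allocation. With duration added, a null drug appears harmful under two codings and mildly beneficial under the third. Splitting a null drug by duration gives apparent benefit in those who completed (0.75 to 0.84) and apparent harm in those who stopped (1.65 to 2.71).

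**4. Baseline quality of life.** If the baseline value correlates r with the 18-month value, adjusting for it removes r² of the variance: 0.5² = 25%, 0.7² = 49%. The document gives no r. Part of this may already be captured by the listed covariates.

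**The case against.** The strongest reply is about scope, and most of it stands.

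- A reader might infer that the primary analysis is biased as planned. It is not. The covariate is offered only as an example, to be used where appropriate, and Section 9.1 fixes the primary model without it. A later statistical analysis plan could decline the option. The subgroup entry has no such escape, because it is already declared prespecified.
- A reader might infer that duration is missing from the whole control side and so almost duplicates allocation. In the ISMN comparison the no-ISMN side includes cilostazol-only participants, who do have time on a trial drug. Strictly, only the group allocated neither drug lacks a value.
- A reader might take the simulated ORs as the expected bias. The stopping rates, the frailty link and the codings are all assumed, and the direction reverses with the coding. Bias also needs stopping to be related to prognosis. Death makes some of that certain, but its size cannot be derived here.
- Duration might be meant as follow-up time, since 6- and 12-month outcomes are also planned. That would be a repeated-measures term, which Section 9.2 covers separately, and not a subgroup.

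Two neighbouring points should not be pressed as errors. Section 9.2 sends "7-level ordinal mRS, 4-level DSM-5 cognitive score, cognitive tests individually (MoCA, TICS") to linear regression. For secondary outcomes at this sample size that is a valid test of a mean difference, so preferring an ordinal model is a matter of choice. Leaving baseline EQ-5D-5L out of the quality-of-life models costs precision but introduces no bias.

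**Conclusion.** The point holds in a limited form. The prespecified subgroup by duration of treatment, and any model that uses the optional duration covariate, would condition on a consequence of allocation and prognosis. That contradicts the intention-to-treat statement in the same section. The argument rests on the document alone: a common planned duration of 18 months, permitted early stopping, death as an outcome level, and a group with no drug and no placebo.

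The size and sign of the bias are not determined by the document. The simulated values show only that they can be material and can go either way. The primary estimate is safe unless the option is taken up. The baseline quality-of-life covariates are a minor efficiency gain of unknown size.

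**What to change.** 1. In Section 9.2, delete treatment duration from the examples of additional adjustment, and delete duration of treatment from the prespecified subgroups.
2. State that covariates and subgroup factors are restricted to variables fixed at baseline. Visible infarct and SVD burden qualify if read from the baseline scan.
3. Report exposure descriptively by arm. If the effect of time on drug is of interest, place it in a separate analysis labelled exploratory and outside intention to treat, with a method suited to post-randomisation exposure such as a complier-average effect.
4. Optionally, add baseline EQ-5D-5L utility and baseline EQ-VAS as covariates in the corresponding 18-month models.

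The cost is wording in Section 9.2, carried into the statistical analysis plan. No data, visits or participants are added. The only loss is the prespecified status of the duration subgroup.
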